4.1.2. Unscheduled Visit

There may be a need to have a subject return to clinic for an unscheduled visit for a variety of reasons, including but not limited to: repeat of a lab test, replacement of IP, or evaluation of an AE. Any procedure that is conducted during a regularly scheduled on-treatment visit may be performed at an unscheduled visit.

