1.3. Schedule of Activities

Procedure	Screening Visit	Randomization													Early Withdrawal from Study	Early Discontinuation of IP	Follow-up (after W16 or EW from study)	Notes
Visit	1	2	2.5	3	3.5	4	4.25	4.5	5	6	7	If needed	If needed	Follow up				
Week	-4 to -2	0	1	2	3	4	5	6	8	12	16	If needed	If needed	20 or as needed		Every visit window +/- 3 days (except for visit 3 which is +/- 2 days); The Screening period includes up to a 4 weeks Run-in period		
Written informed consent	X															Consent form can be obtained prior to Visit 1.		
Demography	X																	
Medical history	X															History of nasal symptoms should be documented. See Section 5.1 inclusion criterion 5.		
Surgical history	X															Specify type of surgery in source document and eCRF.		
Prior treatment history	X															Specify surgery number, type, date.		
Smoking and alcohol use history	X																	
Concomitant medication	X	X	X	X	X	X		X	X	X	X	X	X					
Complete physical examination	X									X	X	X						
Assess presence of nasal polyps	X															Visual assessment to determine presence of nasal polyps by anterior examination.		
Inclusion/exclusion criteria	X																	
Randomization criteria		X																
Efficacy																		
Sino-Nasal Outcome Test-22 (SNOT-22)	X	X				X			X	X	X	X	X					

Procedure	Screening Visit	Randomization	Double-Blind Placebo-Controlled Period										Early Withdrawal from Study	Early Discontinuation of IP	Follow-up (after W16 or EW from study)	Notes
			1	2	2.5	3	3.5	4	4.25	4.5	5	6	7			
Visit	1	2	2.5	3	3.5	4	4.25	4.5	5	6	7	If needed	If needed	Follow up		
Week	-4 to -2	0	1	2	3	4	5	6	8	12	16	If needed	If needed	20 or as needed	Every visit window +/- 3 days (except for visit 3 which is +/- 2 days); The Screening period includes up to a 4 weeks Run-in period	
CT scan		X ₁										X	X*	X*		* Only if it occurs after visit 5. If CT scan cannot be completed on day of visit, it must be completed within 3 calendar days of visit. ¹ Prior to 1 st dose
Nasal endoscopy	X*	X*							X*			X*	X*	X*		*Only in subjects with presence of NP at screening by anterior examination.
Nitric oxide test	X		X						X			X	X	X		Nasal nitric oxide (nNO) and fractional exhaled nitric oxide (FeNO) will be measured.
University of Pennsylvania Smell Identification Test (UPSIT)	X											X	X	X		
Nasal symptoms assessment (review)	X				X				X	X	X	X	X	X		See Section 8.1.4
Visual Analog Scale (VAS)	X				X				X	X	X	X	X	X		

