10.6. Appendix 6: Liver Safety - Actions and Follow-up Assessments

Liver chemistry will be evaluated as specified in the SoA ([Section 1.3](#)) and Appendix 2 ([Section 10.2](#)). Parameters will include ALT, AST, GGT, bilirubin, total bile acids, and ALP.

For subjects with ALT or AST $> 1 \times \text{ULN}$ and $< 3 \times \text{ULN}$ or total bilirubin or direct bilirubin $> 1 \times \text{ULN}$ and $\leq 1.5 \times \text{ULN}$, confirm the value within 24 to 48 hours. Contact the Medical Monitor to determine the appropriate liver monitoring schedule (eg, weekly or twice a week).

The criteria requiring additional liver monitoring with possible interruption of study intervention are detailed in [Table 5](#).

Table 5: Liver Chemistry Criteria Requiring Additional Monitoring with Possible Interruption of Investigational Product

Criterion	Actions
ALT or AST $\geq 3 \times \text{ULN}$ and $< 5 \times \text{ULN}$ or total bilirubin or direct bilirubin $> 1.5 \times \text{ULN}$ without symptoms believed to be related to liver injury or hypersensitivity, and who can be monitored weekly for 4 weeks	
Notify the Medical Monitor within 24 hours of learning of the abnormality to discuss subject safety. “Additional Liver Panel” in Table 6 may be requested by the Medical MonitorConfirm values within 24 to 48 hours via repeat labs. If unable to obtain repeat labs within 48 hours, discontinue IP.Decision to continue or interrupt study intervention will be determined by the Investigator and the Medical MonitorSubject must return weekly or more frequently for repeat liver chemistry tests (ALT, AST, GGT, ALP, total bile acids, and bilirubin) until the abnormalities resolve, stabilize, or return to baseline.If at any time the subject meets liver chemistry interruption criteria (as specified in Table 6), then follow the instructions in “Actions and Follow-up Assessments” in Table 6 and in consultation with the Medical Monitor initiate relevant assessment procedures.

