
 Immediately discontinue IP Report the event to the Medical Monitor within 24 hours Complete the liver event eCRF and complete an SAE data collection tool if the event also met the criteria for an SAE^b Perform liver chemistry follow-up assessments. Monitor the subject until liver chemistry test abnormalities resolve, stabilize, or return to baseline (see MONITORING) Do not restart/rechallenge subject with IP unless Medical Monitor approval is granted If restart/rechallenge not granted, permanently discontinue IP and continue subject in the study for any protocol specified follow up assessments 
MONITORING:
 
 Repeat liver chemistry tests (include ALT, AST, GGT, alkaline phosphatase, total bile acids, bilirubin, and INR) and perform liver event follow-up assessments within 24 hours Monitor subject twice weekly until liver chemistry test abnormalities resolve, stabilize, or return to baseline A specialist or hepatology consultation is recommended 	
Additional Liver Panel
 
 Viral hepatitis serology ^d Obtain INR and recheck with each liver chemistry assessment until the ALT and/or AST values show downward trend Obtain blood sample for pharmacokinetic (PK) analysis Serum creatine phosphokinase (CPK) and lactate dehydrogenase (LDH) Fractionate bilirubin, if total bilirubin $> 2 \times$ ULN Obtain complete blood count with differential to assess eosinophilia Record the appearance or worsening of clinical symptoms of liver injury, or hypersensitivity, on the adverse event (AE) report form Record use of concomitant medications (including acetaminophen, herbal remedies, and other over-the-counter medications) on the concomitant medications eCRF Record alcohol use on the liver event alcohol intake eCRF Anti-nuclear antibody, anti-smooth muscle antibody, Type 1 anti-liver kidney microsomal antibodies, and quantitative total immunoglobulin G (IgG) or gamma globulins Serum acetaminophen assay Liver imaging (ultrasound, magnetic resonance, or computerized tomography) and/or liver biopsy to evaluate liver disease

[figure not shown]

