In general, all analyses will be performed for the overall population, with the exception of efficacy endpoints based on NPS, which will be performed only for the randomized CRSwNP subgroup.

Disposition, demographic and baseline characteristics, significant protocol deviations, and medical history tables will be presented by randomized treatment group and will include an overall column combining both treatment groups. Prior and concomitant medication tables will be presented by either randomized treatment group or actual treatment group, depending on the analysis, and will include an overall column combining both treatment groups. Select analyses among these will be performed for the randomized CRSwNP and CRSsNP subgroups.

Efficacy tables will be presented by randomized treatment group only and select efficacy analyses will be performed for the randomized CRSwNP and CRSsNP subgroups. Safety tables will be presented by actual treatment group and select safety analyses will be performed for the actual CRSwNP and CRSsNP subgroups.

When appropriate, sorting in disposition, demographic, and baseline characteristics tables will be based on decreasing incidence within the overall column. In general, AE tables that are displayed by system organ class (SOC) and preferred term (PT) will be sorted by the internationally agreed order for SOC, and by decreasing incidence and then alphabetically for PT within the GB001 40 mg column. Otherwise, safety tables, when applicable, will be sorted by decreasing incidence within the GB001 40 mg column.

Assessments at the Randomization Visit are to be performed prior to the first dose of study treatment. Therefore, for all measures, the baseline value is defined as either the last non-missing value before the first dose of study treatment, the mean over the last 7 days of the Run-in period including the value on Day 1 (AM endpoints collected in the daily Diary), or the mean over the last 7 days of the Run-in period excluding the value on Day 1 (PM endpoints collected in the Diary).

If multiple evaluations occur on the same day, the average of these evaluations will be used for analysis excluding maximum post-baseline, abnormality, and outlier analyses.

For all shift from baseline analyses, percentages will be based on the number of subjects in each baseline category and also having at least one post-baseline measurement.

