3.1. Visit Windowing

Subjects do not always strictly adhere to the visit schedule timing in protocols. Therefore, the designation of visits (or timepoints) will generally be based on the actual day of evaluation relative to the date of first dose of study treatment (Day 1), rather than the nominal visit, for analyses conducted by visit.

Mutually exclusive visit windows containing no gaps will generally be utilized to assign visits for by visit analysis and will correspond to post-baseline visits specified in the protocol. Visits for analysis will be assigned by using a windowing scheme as described below.

The upper bound of the baseline visit window is Day 1 (up to the time of the first dose for assessments with time collected), and the lower bound of the first post-baseline visit window is Day 1 after the time of the first dose for assessments with time collected and Day 2 for assessments without time collected. For all other lower and upper bounds of visit windows, windows will end at the midpoint between scheduled visit timepoints, with the midpoint in the

latter visit window with the exception of the Week 16 visit for the efficacy endpoints, which will include Day 120 as the upper bound of the visit window.

If a subject's last observation is after the date of first dose of study treatment but prior to the first scheduled visit, data from an EW visit will be assigned to the first scheduled visit. If two or more evaluations occur in the same visit window, the evaluation closest to the target visit day will be selected for inclusion in the analysis. If multiple evaluations are equally close to the target visit day, then the latest evaluation will be selected for inclusion in the analysis. The target visit day for Week 1 and on is defined as the week number specified in the SoA of the protocol multiplied by 7 plus 1.

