9.2. Clinical Laboratory Evaluation

Actual values and change from baseline values for quantitative laboratory parameters (clinical and liver chemistry, hematology, and urinalysis) will be summarized by visit for the safety population.

Shift tables will be presented for clinical and liver chemistry, hematology, and qualitative urinalysis parameters summarizing shifts from baseline to high and low (or to abnormal for urinalysis) at any time post-baseline based on laboratory normal ranges.

A summary of maximum post-baseline values > 1.0 , > 1.5 , and $> 3.0 \text{ } 10^9/\text{L}$ for blood eosinophils will be presented.

Summaries of maximum post-baseline values for liver chemistry parameters (alanine aminotransferase [ALT], aspartate aminotransferase [AST], ALT or AST, concurrent ALT or AST and total bilirubin, total bilirubin, direct bilirubin, indirect bilirubin, alkaline phosphatase, gamma-glutamyl transferase [GGT]), and bile acid according to categories based on multiples of upper limit of normal (ULN) will be presented. Liver chemistry parameters according to categories based on multiples of ULN will also be presented by visit.

For laboratory shift tables and summaries of maximum post-baseline values, only subjects with at least one post-baseline value will be included.

The time to first elevation for ALT will be presented for subjects with an elevation in ALT. An elevation for ALT will be defined as the first post-baseline value $\geq 1.5 \times \text{ULN}$ for subjects with a baseline value $\leq \text{ULN}$, and the first post-baseline value with a $> 50\%$ increase from baseline for subjects with a baseline value $> \text{ULN}$. This analysis will also be repeated using a threshold of $> 1.0 \times \text{ULN}$. In addition, the time to first elevation of AST will be summarized in the same manner as described above for time to first elevation of ALT.

In addition, the following figures/plots will be provided:

- Mean change from baseline values, including SE bars, by visit figures for liver chemistry parameters
- Mean ratio of actual values to ULN, including SE bars, by visit figures for liver chemistry parameters
- Evaluation of Drug-Induced Serious Hepatotoxicity (eDISH) ([Merz, 2014](#)) plots

- Mean actual values and mean change from baseline values, including SE bars, by visit figures for blood eosinophils
- Maximum post-baseline values versus baseline values plot for blood eosinophils

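### By-visit liver outputs can lose an elevated scheduled value to its own repeat when the visit was a few days early: a small, avoidable selection effect

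*Protocol*

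**What the plan says.** **When repeats are taken.** Protocol Appendix 6 (Section 10.6) ties repeat liver chemistry to elevation. For ALT or AST between 1 and 3 x ULN, or a modest bilirubin rise, the site must "confirm the value within 24 to 48 hours". Table 5 sets the same 24-48 hour interval for ALT or AST from 3 to below 5 x ULN. Once a Table 6 criterion is met, the site must repeat the chemistry and "perform liver event follow-up assessments within 24 hours". Section 4.1.2 foresees unscheduled visits for reasons "including but not limited to: repeat of a lab test, replacement of IP, or evaluation of an AE". A normal value triggers no repeat.

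**When visits occur.** The Schedule of Activities allows "Every visit window +/- 3 days (except for visit 3 which is +/- 2 days").

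**Which value is used.** SAP 3.1 assigns values to visits by actual day relative to first dose, not by nominal visit, with a target day of 7 x week + 1. If a window holds several values, "the evaluation closest to the target visit day will be selected for inclusion in the analysis". If they are equally close, "then the latest evaluation will be selected for inclusion in the analysis". The section does not separate scheduled from unscheduled samples. For several values on one day, SAP 3 says "the average of these evaluations will be used for analysis excluding maximum post-baseline, abnormality, and outlier analyses".

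**Where it is used.** SAP 9.2 summarises laboratory values and changes by visit, plans by-visit figures of mean change and mean ratio to ULN, and adds: "Liver chemistry parameters according to categories based on multiples of ULN will also be presented by visit".

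**The concern.** Whether a second sample exists depends on the first result. An elevated scheduled value brings a repeat that competes for the same window; a normal value does not. Where the repeat wins, an elevated value leaves the by-visit output and whatever the repeat showed takes its place. No opposite process replaces normal values.

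The Protocol treats liver injury as a potential risk, reports two Hy's Law cases in the programme, and requires screening ALT and AST at or below 1 x ULN. Values above ULN on treatment are therefore of direct interest. The by-visit ULN categories show how many subjects are elevated at each time point in each arm. If that count is trimmed, it is trimmed more, in absolute numbers, in the arm with more elevations. The table may then disagree with the maximum and shift tables for reasons unrelated to the drug.

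**Working it through.** The plan gives no figure for this, so there is none to reproduce.

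**1. When the repeat wins.** Let *d* be the scheduled draw's offset from target in days and *k* > 0 the days from draw to repeat. The repeat is used if it is closer or tied: |d + k| <= |d|. Squaring gives 2dk + k² <= 0, so **d <= -k/2**. The scheduled draw must precede the target day. The weekly windows in SAP 3.1 run from target -3 to target +3 or wider, so a repeat meeting this condition is always in the same window.

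**2. How often.** Visit days are assumed uniform over the allowed range; the documents do not give their distribution.

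| Repeat after draw | Offsets replaced | Share, +/- 3 days | Share, Visit 3 (+/- 2 days) |
|---|---|---|---|
| 1-2 days | -3, -2, -1 | 3/7 = 43% | 2/5 = 40% |
| 3-4 days | -3, -2 | 2/7 = 29% | 1/5 = 20% |
| 5-6 days | -3 | 1/7 = 14% | 0 |
| 7 days or more | none | 0 | 0 |

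The first row is 6 of the 14 combinations of seven offsets and two gaps. With visits centred on target (assumed weights 0.05, 0.10 and 0.15 at -3, -2 and -1), the 1-2 day share is 30%. It is 0% if all visits fall on or after target and 100% if all are early.

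**3. Direction of the count.** For the parameter that triggered the repeat, the replaced value is above 1 x ULN by definition. The repeat is either above (count unchanged) or not (count falls by one). This needs no distributional assumption, but it covers only the count above 1 x ULN. A repeat can be higher than the value it replaces, so higher categories and means can move either way.

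**4. Size.** Log ALT/ULN was simulated with an assumed between-subject SD of 0.35, uniform visit days and repeats at 1-2 days.

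- No trend, within-subject SD 0.15-0.25: 15% above ULN is shown as 11.8-12.8%, and 5% as 3.6-4.0%. With 50 per arm, that is (15 - 12.8)% x 50 = 1.1 to (15 - 11.8)% x 50 = 1.6 subjects, and 0.5 to 0.7 subjects. A 10-point difference becomes 12.8 - 4.0 = 8.8 to 11.8 - 3.6 = 8.2 points, a loss of 0.6 to 0.9 subjects.
- No trend, median ALT 0.5-0.7 x ULN, within-subject SD 0.1-0.3: from 2.9% to 2.4% at the low end (0.2 subjects) and from 21.9% to 17.3% at the high end (2.3 subjects). Means fall by about 0.1% to 3%.
- ALT rising about 20% between draws: the mean goes up in 4 of 6 scenarios (for example 0.748 to 0.763 x ULN). The share above ULN still falls slightly, for example 16.3% to 16.1%.
- ALT falling by a similar amount: larger drops, at most 22.0% to 15.5% (3.2 subjects).

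Without a trend, the loss scales with the share in step 2. Repeats at 3-4 days give two thirds of it, so 15% loses 0.7 to 1.1 subjects; repeats at 5-6 days give one third.

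**The case against.** The strongest reply is that nothing important about liver safety depends on these outputs. SAP 9.2 also plans maximum post-baseline values by ULN multiple, including ALT or AST with concurrent bilirubin, shifts at any time, eDISH plots, and time to first elevation of ALT and AST at two thresholds. SAP 3.1 governs by-visit analyses only, so all of these keep the elevated scheduled value, as do the listings. Onset has its own analysis, and no hypothesis test is specified for laboratory data. This stands, and it limits the point to the by-visit outputs.

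The replacement share is also uncertain. Appendix 6 does not say whether 24-48 hours runs from the draw or from receipt of the result, and samples go to a central laboratory. If the clock starts at the result, the slower rows of the table apply. This stands too.

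A reader might infer that repeats generally displace elevated values, or that by-visit liver means are biased low. The documents support neither. Draws on or after target keep their value, Table 6 events have a 24-hour limit instead of 24-48 hours (a same-day repeat falls under the averaging rule), and a rising ALT gives a higher repeat.

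Finally, the exemption in SAP 3 concerns same-day averaging, a different rule, so SAP 3.1 does not contradict it. What remains is that SAP 3.1 lets a result-triggered sample displace the scheduled one.

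**Conclusion.** The point holds as a minor one. Under SAP 3.1, an elevated scheduled liver value drawn 1-3 days early can be replaced in by-visit outputs by a repeat taken only because it was elevated. For these replacements the count above 1 x ULN cannot rise. Means are likely lowered if values are stable or falling, but not if they are rising.

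The size is about one subject per arm per visit or less at plausible rates. It is somewhat more with fast repeats and 15% or more of subjects above ULN, and nil where visits are on or after target. These sizes rest on assumed visit-day distributions, repeat timing and ALT variability, none of which the documents give. The one-way effect on the count follows from the rules alone.

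It would be tempting to conclude that the plan hides a liver signal. It does not: peak, any-time shift and onset analyses are untouched.

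**What to change.** Add one sentence to SAP 3.1, with a cross-reference in 9.2: by-visit liver chemistry summaries, ULN categories and figures use the scheduled-visit sample when one exists in the window, and an unscheduled repeat only when none does. State that repeats stay in the maximum, shift, eDISH and time-to-first-elevation outputs and in the listings.

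Taking the highest value in the window for the ULN categories is a possible alternative, but it has its own selection problem. Appendix 6 has elevated subjects sampled weekly or twice weekly, so a window up to four weeks wide gives them more chances of a high value. The scheduled sample avoids this.

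The cost is one sentence and minor programming. It needs no new data and changes neither the Protocol nor subject management.

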4.2. Scientific Rationale for Study Design

4.2.1. Study Population

The study population is comprised of: symptomatic CRS subjects with CRSsNP, defined as an absence of NP based on visual examination or an NPS of 0 based on nasal endoscopy, and evidence of an eosinophilic phenotype (eCRS), defined as a blood eosinophil count of ≥ 250 cells/ μ L; and symptomatic CRS subjects with CRSwNP, defined as a minimum NPS of 4 out of a maximum of 8, with at least a score of 2 for each nostril, as assessed by endoscopic diagnosis by a blinded central reader. Subjects with historical evidence of neutrophilic predominant polyp disease will be excluded considering that the mechanism of action of GB001 is thought to be linked to eosinophilic Type 2 inflammation. The overall study population will consist of approximately 64 CRSwNP subjects and 36 CRSsNP subjects.

GB001 will be administered as an additional treatment on top of a stable standard of care (SOC) regimen of mometasone furoate nasal spray (MFNS).

4.2.2. Choice of Control Group

All subjects will be on background SOC. The study is placebo-controlled to minimize bias and provide an inactive control group to which the efficacy of GB001 can be compared. Comparisons between the GB001 and placebo treatment groups will facilitate differentiation of the GB001 safety profile from that of the SOC. Lastly, a placebo group, as opposed to an active control, will help to understand whether the occurrence of an AE in the GB001 group is different from that which would occur in this population in the absence of GB001.

4.2.3. Efficacy Endpoint Selection

The primary endpoint is the change from baseline to Week 16 in SNOT-22. This instrument has been used in multiple clinical studies to demonstrate the impact of different types of treatment interventions in subjects with CRS.

In addition, this study will explore the impact of GB001 on bilateral nasal polyps and associated sinus symptoms, using specific assessments and questionnaires.

